5.13. Health care resource use

The feasibility of collecting health care resource use over the 28 days post randomization will be assessed but no formal analysis is proposed for the pilot study

5.14. Cost-effectiveness

There are no plans to perform cost-effectiveness analysis for the feasibility study, but will be performed for the main trial

5.15. Sample size calculation

Feasibility estimates: to estimate follow-up rates between 65% and 80% assuming we want to be reasonably sure that the follow-up rate is not 50% in each group (i.e.95% confidence intervals of +/- 15%) then 41 per group are needed. We anticipate that it should be possible for the intervention group to achieve use of antibiotics of around 65% or less. To estimate this proportion with 95% confidence intervals of +/- 15% (i.e. to be sure the use of antibiotics is 80% or less) 41 per group is also needed.

Provisional estimates of antibiotic reduction. In addition to descriptive information of antibiotic in each group we can also provide very provisional estimates of the difference in antibiotic use compared with control: 43 individuals per group will detect a plausible 25% absolute reduction in antibiotic use (for alpha=0.05 and 80% power) to 65% assuming at least 90% of the control group use antibiotics. Allowing for 20% loss to follow-up we will recruit 108 participants.

5.16. Feasibility

In our previous one centre study we were able to assess and randomise 238 individuals who fulfilled the Berg and Carenfeldt criteria in 4 years with a full time RA, but recruitment in primary care in the current context is more challenging than previously. A GP will also not see a case of sinusitis every day so full time staff are difficult to justify in all centres. If the coordinating centre has a P/T trial manager to coordinate, and each centre has some RA support and part time administrative help, this should allow us to recruit our target in 2 winters.

5.17. Role of funders

The funder will have no role in data collection, analysis, data interpretation, report writing or in the decision to submit for publication.

5.18. Nested qualitative study

AIMS:

To explore a range of patient views on study participation, seeking to understand positive and negative experiences from start to finish.

TIMING:

Will take place once participants have been randomized and participated.

METHODS:

Semi-structured in-depth interviews will be used, but will be flexible to permit patients to speak freely on topics they deem to be relevant to ensure key emerging issues are captured. A subtle realist approach will be employed throughout the project to help represent participants' views.

SAMPLE:

A purposive sampling approach will be designed to elicit views of a range of patients (including a mix of men and women/rural and urban settings).Between 15 and 30 interviews should be adequate to represent the views of a range of patients following participation. Additional interviews will be conducted if saturation has not been reached.

ANALYSIS:

We will follow the stages of Braun and Clarke's thematic analysis, assisted by NVivo (QSR international Pty Ltd) computerized analysis software as necessary. Analysis will aim to identify themes to help fulfil aims 1 and 2 whilst remaining flexible and open to emerging findings.

QUALITY:

Standard methodological strategies will be employed to help safeguard rigour and ensure we produce trustworthy, plausible, and relevant findings. These will include careful purposive sampling, a clear exposition of methods (including field notes, and audio recording of interviews and accurate transcription of interviews, regular discussion between the fieldworker and senior qualitative researcher (including double coding/discussion of codes). Negative case analysis will help to refine analysis/safeguard against premature completion and the researcher will be tutored in the importance of a 'reflexive' sensitivity to the relationship between the researcher and research process.

CONFIDENTIALITY:

We will abide by the University of Southampton's Data Protection Compliance Statement. The University of Southampton (the University) is a research-led university that takes its data protection responsibilities seriously. We support the aims of data protection legislation to strengthen the rights of

individuals in respect of data relating to them and we are committed to complying with our obligations when processing personal data (either as a data controller or as a data processer).

Interviews will be recorded, transcribed and destroyed on completion of transcription and then stored in accordance with the University's archiving process, which is 10 years. All data will be anonymised and/or stored on password protected and secure drives.

5.19 Discontinuation / withdrawal of participants from trial

Each participant has the right to discontinue their study medication or withdraw from the study at any time. In addition, the investigator may discontinue a participant's treatment or withdraw a participant from the study at any time if the investigator considers it necessary (e.g. the participant experiences an adverse reaction, the patient withdraws consent, or the investigator considers that further participant in the study would not be appropriate due to the personal circumstances of the participant).

Patients whose nasal irrigation is discontinued will still be required to complete their study diaries and questionnaires and will still receive telephone follow-up calls unless they choose to withdraw consent for these.

WITHDRAWAL

Once a participant withdraws or is withdrawn from the study, no actions will be taken to obtain data other than to monitor adverse events (see section 7.3. PROCEDURES FOR RECORDING ADVERSE EVENTS). Consent to proceed with reviewing the medical notes will be specifically confirmed for participants withdrawn from the study.

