6.3. Compliance with Trial Treatment

Patients will be asked to record in their study diaries each time irrigation was used. Patients whose study diaries indicate that they received more than half the intended irrigations during the first week will be considered to be compliant with trial procedures. All randomised trial participants will be included in the intention-to treat population.

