9.4. Inclusion in Analysis

The primary analysis will be an intention to treat basis. A per protocol analysis is unlikely to be very meaningful in the proposed modest sample but we can present estimates for individuals who irrigate more than 50% of the days during the first week.

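### Section 5.19 ends diary, questionnaire and telephone follow-up for participants the investigator withdraws, even if they have not refused it, and promises continued follow-up only when irrigation is stopped

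*Protocol*

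**What the plan says.** Protocol Section 5.19 has two tiers.

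- **Stopping treatment.** "Patients whose nasal irrigation is discontinued will still be required to complete their study diaries and questionnaires", and telephone calls also continue, unless the patient withdraws consent for these. The sentence names irrigation only.
- **Leaving the study.** "Once a participant withdraws or is withdrawn from the study, no actions will be taken to obtain data other than to monitor adverse events". For notes review, "Consent to proceed with reviewing the medical notes will be specifically confirmed for participants withdrawn from the study".

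The investigator can apply either tier: "the investigator may discontinue a participant's treatment or withdraw a participant from the study at any time if the investigator considers it necessary". The examples given cover both: "the participant experiences an adverse reaction, the patient withdraws consent, or the investigator considers that further participant in the study would not be appropriate" because of personal circumstances.

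Other sections bear on this:

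- Section 1 names antibiotic use as the primary outcome. Section 5.12 takes it from the four-week diary. Section 5.11 adds a brief questionnaire, then a phone call or text, for those who return no diary.
- Section 4 makes the follow-up rate part of the pilot's aim, and Section 5.12 lists follow-up with a primary outcome, by group, as a feasibility outcome.
- Section 6.3: "All randomised trial participants will be included in the intention-to treat population". Section 9.4: "The primary analysis will be an intention to treat basis".
- Section 9.3 allows multiple imputation for the regression analyses if appropriate.

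**The concern.** The rule on ending data collection does not separate a participant who refuses further contact from one whom the investigator removes. For the second there is no consent-based reason to stop asking for the diary or to omit the brief questionnaire and call.

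Two things are at stake. First, an adverse reaction is a listed ground, and reactions to antibiotics and to irrigation arise from different treatments, so losses may differ by arm and be related to the outcome. That would distort the comparison of antibiotic use and symptom duration. Second, the follow-up proportion is meant to inform a full-trial application. Each participant dropped under this rule lowers it by protocol, not because the patient failed to respond, so it would say less about what a full trial could achieve.

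**Working it through.** **1. What the text does to each type of participant**

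| Situation | Diary, questionnaire, calls | Notes review |
|---|---|---|
| Irrigation stopped, stays in study | Continue unless consent for these is withdrawn | As planned |
| Control patient stops antibiotics, stays in study | Not stated | As planned |
| Withdrawn by the investigator, either arm | Stop | Only if consent is confirmed |
| Withdraws from the study, either arm | Stop | Only if consent is confirmed |

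The third row is the problem. An adverse reaction can lead to the first row or the third, and nothing tells the investigator which applies.

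**2. What notes review can recover.** Section 5.12 takes reconsultation and resource use from the notes, and Section 6.5 takes further antibiotics and other medications prescribed over 28 days. Whether the original immediate or delayed prescription was used, symptom duration and EQ5D come from the participant and are lost.

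**3. The plan's own sample size (Section 5.15).** Inputs: 90% versus 65%, alpha 0.05 (taken as two-sided), 80% power, 20% loss. With a pooled proportion of 0.775:

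n = [1.96 × √(2 × 0.775 × 0.225) + 0.84 × √(0.90 × 0.10 + 0.65 × 0.35)]² / 0.25² ≈ 42.6, so 43 per group.

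2 × 43 / 0.80 = 107.5, so 108 in total, or 54 per arm with 54 − 43 = 11 losses allowed in each. The stated figures reproduce, and this point changes none of them.

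**4. Illustrative size.** The protocol gives no withdrawal rate. Assume 3 or 5 of 54 irrigation patients are withdrawn by the investigator, all had used antibiotics, and there is no other loss. Expected users are 0.65 × 54 = 35.1 with irrigation and 0.90 × 54 = 48.6 in control. The true difference is 25 points.

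Losses in the irrigation arm only:
- 3 withdrawn: 32.1/51 = 62.9%; difference 90 − 62.9 = 27.1 points, a shift of 2.1.
- 5 withdrawn: 30.1/49 = 61.4%; difference 28.6 points, a shift of 3.6.

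The same number of antibiotic users also withdrawn from control:
- 3 per arm: 45.6/51 = 89.4%; difference (48.6 − 35.1)/51 = 26.5 points, a shift of 1.5.
- 5 per arm: 43.6/49 = 89.0%; difference 13.5/49 = 27.6 points, a shift of 2.6.

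These losses overstate the reduction in antibiotic use. If some of those withdrawn had not used antibiotics, the shift would shrink and could reverse.

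**5. Follow-up.** Three withdrawals leave 51/54 = 94.4% and five leave 49/54 = 90.7% before any other loss. They would use 3 to 5 of the 11 losses allowed in that arm.

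**The case against.** The strongest reply is that Section 5.19 already separates stopping treatment from leaving the study, and keeps irrigation patients in follow-up after the first. An adverse reaction would most naturally lead to stopping treatment, so the damaging route is permitted but not directed. Follow-up lasts 28 days, Section 7 reports no serious side effects of irrigation, and such withdrawals may be few. The between-group analysis is labelled exploratory in Section 9.1, and a shift of 2 to 4 points is small beside the planned precision of ±15 points per group. All of this stands and limits the importance of the point. It does not remove the rule, which still ends follow-up for people who have not refused it.

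Multiple imputation is a weaker reply. Standard imputation does not cure loss that depends on the unobserved outcome, and it leaves the descriptive follow-up proportion unchanged.

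A reader might infer three stronger things that the documents do not support:

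- *That all outcome data cease.* Notes review remains possible with confirmed consent.
- *That the rule contradicts the intention-to-treat statements.* Sections 6.3 and 9.4 define who is analysed by randomisation. A missing outcome removes nobody from that population; it is a missing-data limitation.
- *That control patients who stop antibiotics are dropped by rule.* The protocol is silent about them, and irrigation patients withdrawn from the study are equally unprotected. This is a gap in the wording.

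**Conclusion.** The point holds in a limited form. Section 5.19 stops participant-reported follow-up for anyone the investigator withdraws, whether or not that person has refused it, and states continued follow-up only for stopped irrigation. The resulting loss may be related to treatment and outcome, and it lowers by rule a proportion that the pilot is designed to estimate.

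The size is unknown and probably small. The illustrated shift of about 2 to 4 points rests on an assumed 3 to 5 withdrawals in the irrigation arm, all antibiotic users, with none in control; equal losses in both arms reduce it to about 1.5 to 2.6 points. The sample size is unaffected. The change is worth making because it is cheap and because an analysis plan cannot recover data that the protocol says not to seek. It is not a threat to the validity of the pilot as a whole.

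**What to change.** Amend Section 5.19 as follows:

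1. State that, in both arms, stopping the allocated treatment or an investigator decision to discontinue does not end diary, brief questionnaire or call and text follow-up, unless the participant withdraws consent for that data collection.
2. Limit the rule that no further data are sought to participants who withdraw that consent.
3. Keep the existing step of confirming consent for notes review. Replacing it would be an ethical preference, not a correction.
4. Report investigator withdrawals, with reasons, by arm.

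None of this alters the investigator's freedom to stop treatment. The cost is a few sentences in Section 5.19 and matching wording in the information sheet, with no additional patients or visits.

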5.20 Definition of end of trial

The end of the trial will be the date of the last medical notes review of the last trial participant.

5.21 Thank you to patients

As a token of our thanks for helping with the study and the time doing the diary we will provide a £10:00 High Street shopping voucher.

6. NASAL IRRIGATION

6.1. Saline Description/delivery

Intervention component	Dosage form/method
SinuCleanse 19 nasal cup	Irrigate the nose (150 ml through
('Netipot') will be provided to each	each nostril) daily for up to 21 days
subject.	or until symptoms settle

	Patients will make their own buffered saline irrigation solution
	heaped teaspoon salt, one half
Buffered saline	(568 ml) tap water; how to do this will also demonstrated on the
	video clip.

TREATMENT BLINDING

Patients cannot be blinded to treatment allocation throughout the trial.

6.2. Storage of Saline

If Saline is made fresh every 1-2 days there is no need for special storage arrangements.

6.3. Compliance with Trial Treatment

Patients will be asked to record in their study diaries each time irrigation was used. Patients whose study diaries indicate that they received more than half the intended irrigations during the first week will be considered to be compliant with trial procedures. All randomised trial participants will be included in the intention-to treat population.

6.4. Monitoring Trial Treatment

The investigator or designee must maintain an accurate record of the provision of Netipots, salt and bicarbonate in the baseline CRF (to be completed during the consultation). The CRFs will be monitored for completeness by the RA or administrator running the trial, and missing data requested from clinicians.

6.5. Concomitant Medication

Trial participants will be advised to continue their usual regular medications while taking part in the trial. Healthcare professionals will record data at baseline on antibiotic prescriptions given during the consultation, also any other prescriptions (e.g. inhalers, analgesics). We will advise clinicians to prescribe an appropriate betalactam antibiotic when prescribing as a first line agent (unless allergic to beta-lactams in which case a macrolide will be advised).

Patients will be advised that they can take over the counter medications for their sinusitis (e.g. analgesics). They will be asked to record these additional medications in the study diary from days 1 to 28.

Clinicians will treat trial participants who re-consult in whatever way they feel is clinically appropriate.

A member of the research team will provide the practice staff with instructions for extraction of data and a form to record the data from participants' medical notes on further antibiotics and other medications prescribed during the 28-day period after study entry.

6.6. Post-trial Treatment

Participants will only be asked to use nasal irrigation for the duration of the current episode of sinusitis. After this they can use nasal irrigation if they wish, based on the prior evidence of a preventive effect for chronic/recurrent sinusitis.

7. SAFETY REPORTING

All adverse events, for patients randomised into the trial, should be reported from the time the patient signs the informed consent form until one week after randomisation. Depending on the nature of the event the reporting procedures below should be followed.

Any questions concerning adverse event reporting should be directed to the Study coordination centre in the first instance. A flowchart will be provided to aid in the reporting procedures.

Adverse events presenting to the participants GP will be notified by the practitioner. In addition participants will carry a study card which highlights the need to notify their own doctor regarding adverse events. As a final check all participants will be asked to consent to a medical notes review which will take place after study recruitment at a time when any letters will have been returned from out-patient appointments. This enables us to be confident of detecting adverse events which have not been notified using the first two mechanisms. A member of the research team will provide the practice staff with instructions for extraction of data and a form to record the data from participants' medical notes on further antibiotics and other medications prescribed during the 28-day period after study entry.

Adverse Event (AE)	Any untoward medical occurrence in a participant to whom a		
	medicinal product has been administered, including occurrences		
	which are not necessarily caused by or related to that product.		
	These will not be collected for this study.		
Adverse Reaction (AR)	An untoward and unintended response in a participant to an		
	investigational medicinal product which is related to any dose		
	administered to that participant.		
	The phrase "response to a trial intervention" means that a causal		
	relationship between a trial intervention and an AE is at least a		
	reasonable possibility, i.e. the relationship cannot be ruled out. All		
	cases judged by either the reporting medically qualified professional		
	or the Sponsor as having a reasonable suspected causal		
	relationship to the trial qualify as adverse reactions.		
Serious Adverse Event	A serious adverse event is any untoward medical occurrence that:		
(SAE)	results in death		
	is life-threatening		
	 requires inpatient hospitalisation (i.e an overnight stay) or 		
	prolongation of existing hospitalisation		
	 results in persistent or significant disability/incapacity 		
	 consists of a congenital anomaly or birth defect. 		
	Other 'important medical events' may also be considered serious if		
	they jeopardise the participant or require an intervention to prevent		
	one of the above consequences.		

	NOTE: The term "life-threatening" in the definition of "serious" refers	
	to an event in which the participant was at risk of death at the time	
	of the event; it does not refer to an event which hypothetically might	
	have caused death if it were more severe.	
Serious Adverse Reaction	An adverse event that is both serious and, in the opinion of the	
(SAR)	reporting Investigator, believed with reasonable probability to be due	
	to the trial treatments, based on the information provided.	

Hospitalisations for elective treatment of a pre-existing condition do not need reporting as Serious Adverse Events (SAEs).

The antibiotics used in SNIFSII (beta-lactams or macrolides) are licensed medicines whose most common side-effects are mucocutaneous candidosis (thrush), diarrhoea, nausea, vomiting and rash (occurrence >=1/100 to <1/10). If these occur and are non-serious and of mild to moderate severity (based on clinician's assessment) an Adverse Event Report form will not be necessary. We will collect data on events such as severe reactions to the antibiotics such as anaphylaxis, severe allergy requiring steroid administration, emergency hospitalization for chest problems and severe Clostridium (antibiotic related diarrhoea).

Unexpected adverse reactions to antibiotics will be highly unlikely amongst trial participants, as the vast majority of patients will have previously received antibiotics to treat other infections. For non-serious adverse reactions to trial medication, the Chief Investigator or a designated alternative study clinician will assess the urgency with which the participant's treatment allocation should be unblinded.

For Nasal Irrigation there have been no serious sides effects reported, the most common side effects being nasal stinging and sinus discomfort for some patients.

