5.7. Intervention

1) Control group: immediate antibiotic prescription. We wish to provide some estimate of the reduction in antibiotic possible compared with current practice. Since more than 90% of patients currently receive antibiotic for acute sinusitis the nearest approximation to usual care is a prescription for immediate antibiotics, combined with advice about the use of analgesics. Although the particular antibiotics used is not the focus of this investigation, in line with PHE guidance for primary care we will advise the use of Penicillin V 500mgs QDS (or alternatively Amoxicillin 500mg tds) for 1 week or Clarithromycin 500mg BD also for 1 week if participants are allergic to penicillin.

2) Advice to use nasal irrigation. In addition to the advice in the usual care arm to use simple analgesics participants will be given both written and verbal instructions and given a link to a video clip (uploaded on YouTube: http://www.youtube.com/watch?v=zgvoxkGYSU4) demonstrating how to perform irrigation. They will be asked to irrigate the nose (150 ml through each nostril) daily for up to 21 days or until symptoms settle, and a SinuCleanse 19 nasal cup ('Netipot') will be provided to each subject. Patients will make their own buffered saline irrigation solution every 1 to 2 days comprising: 1 heaped teaspoon salt, one half teaspoon baking soda and 1 pint (568 ml) tap water; how to do this will also demonstrated on the video clip. We chose this particular intervention based on the provisional evidence from a previous randomised controlled trial in primary care in chronic/recurrent sinusitis (11) and from our most recent large trial also in chronic or recurrent sinusitis (13), where most patients found it acceptable and the majority continued using nasal irrigation. Participants in this group will be offered a delayed antibiotic prescription as in our previous trials(19), and advised only to use it if symptoms are getting significantly worse or not even starting to settle a little after a further week.

All study participants in both groups will have access to usual care; further medication or referral will be at the discretion of the doctor according to the normal practice of that doctor.

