- Duration of moderately bad illness. The duration of illness rated moderately bad or worse i.e. making an important difference to patients, and as used in our previous studies of respiratory infections (20, 21). It will be measured using the symptom diary and where the diary is not returned information from a brief follow-up questionnaire, and/or phone call as necessary. The 4 week diary includes 11 symptom variables, assessed on 7 point Likert scales. The score has been developed to have content validity by incorporating items which not only take account of proposed diagnostic criteria for bacterial rhinosinusitis(22) but also physicians' perceptions of the important clinical features (based on focus groups and a questionnaire study)(23). The format of the diary items has been developed in a variety of other respiratory infections and been shown to have construct and criterion validity, and also sensitivity to change.(8, 17, 24) We have also shown the total symptom score for sinusitis is internally reliable (Cronbach's alpha 0.77) and sensitive to change (standardized response mean 1.6 comparing day 0 with day 5).(8, 24)
- The duration of any symptom until rated very little or no problem (measured as above);
- **Reconsultation** with non-resolving, new, or worsening illness within 1 month of the index consultation documented from medical records, and which can be measured reliably(25);
- EQ5D5L (at days 1,7,14,21,28 of the diary). In prior trials EQ5D has been shown to be adequate in detecting the decrement in QOL with RTIs to allow cost-effectiveness modelling(26) should the main trial be funded;
- **Resource use.** Information on NHS resource usage will be collected for all participants from a notes review including capturing resource use for rare major adverse events (e.g. anaphylaxis, complications, hospital admission) up to 28 days.

- Self-reported adherence and reasons for non-adherence, using the validated Problematic Experiences of Therapy Scale, across different aspects of intervention materials (written / video / online instructions).
- Modified Patient Enablement Instrument(27)

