7.3. Procedures for Recording Adverse Events

The side effects of interest will be collected through the completion of the daily diary only.

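### Adverse-event reporting stops one week after randomisation, which spans the control arm's antibiotic course but not all of the intervention arm's irrigation or delayed antibiotics, and Section 7 contradicts itself on what is collected

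*Protocol*

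**What the plan says.** The opening of Protocol Section 7 states that all adverse events in randomised patients "should be reported from the time the patient signs the informed consent form until one week after randomisation", and then directs the reader to the procedures below it. Section 7.4 asks practices to report serious adverse events within 24 hours of awareness. It gives no separate end date, and neither does the flowchart in Appendix E.

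Treatment runs on different clocks in the two arms (5.7):

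- Control: "Control group: immediate antibiotic prescription", with the course given "for 1 week or Clarithromycin 500mg BD also for 1 week if participants are allergic to penicillin".
- Intervention: irrigation "daily for up to 21 days or until symptoms settle", plus a delayed prescription that participants are "advised only to use it if symptoms are getting significantly worse or not even starting to settle a little after a further week".

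Other sentences bear on what is recorded. The adverse-event row of the Section 7 definitions table says "These will not be collected for this study". Section 7.3 says "The side effects of interest will be collected through the completion of the daily diary only". The text after the table promises data on severe antibiotic reactions such as anaphylaxis and severe Clostridium diarrhoea. The resource-use item among the secondary outcomes (5.12) relies on a notes review that captures resource use for "rare major adverse events (e.g. anaphylaxis, complications, hospital admission) up to 28 days". Section 7 also names GP notification, a study card and a notes review as ways to detect events.

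**The concern.** A reporting window should span the period in which participants are exposed to the trial treatments. This one has the same length in both arms, but exposure begins and ends at different times. The control arm's planned antibiotic course fits inside it. The intervention arm's irrigation can continue for two more weeks, and a delayed course may begin only as the window shuts.

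The Trial Steering Committee reviews serious adverse events after each recruitment season and may advise on termination (7.7, 7.9, 11). If practices follow Section 7 literally, a serious event on day 10 in someone still irrigating, or newly on the delayed antibiotic, need not reach that review through practice reporting. The pilot is meant to support a full-trial application, so a faulty harms procedure could carry forward.

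The wording conflict is a separate problem. A practice cannot both report all adverse events and treat them as not collected.

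**Working it through.** The plan gives no figure for harms coverage, so there is none to reproduce. The check overlaps the reporting window with planned exposure.

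**Inputs.** Window W = 7 days from randomisation (Section 7). Antibiotic course C = 7 days in either arm; 5.7 states one week for the advised antibiotics, and the same length is assumed for a delayed course. Irrigation I = up to 21 days (5.7). Delayed course starts s days after randomisation; 5.7 gives two triggers, and no start-time distribution is stated.

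**Antibiotic days in the window** = max(0, min(s + C, W) − s), which with C = W = 7 is max(0, 7 − s).

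| Course | Start s | Days in window |
|---|---|---|
| Control, immediate | 0 | 7 of 7 |
| Delayed, started early for worsening | 2 | 5 of 7 |
| Delayed, started early for worsening | 4 | 3 of 7 |
| Delayed, started early for worsening | 6 | 1 of 7 |
| Delayed, after the advised week | 7 or later | 0 of 7 |

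Any start after the day of randomisation covers less than a full course, so the shortfall always falls on the delayed course. Its size depends on start times that the protocol does not give.

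**Irrigation days in the window** = min(I, W) / I. At the full 21 days this is 7/21 = 33%, with 21 − 7 = 14 days outside. If irrigation stops at 14 days it is 7/14 = 50%; at 7 days or fewer it is complete.

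**With a 28-day window.** Irrigation: 21 of 21 days. Control antibiotics: 7 of 7. A delayed course is covered in full if s + 7 ≤ 28, that is, if it starts up to 21 days after randomisation.

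**The routes side by side.**

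| Route | Stated period | Limit |
|---|---|---|
| Practice reports (7, 7.4) | Consent to one week after randomisation | Ends before much intervention-arm exposure |
| Diary (5.11, 7.3) | Up to four weeks, both arms | Posted back once symptoms settle; cannot give 24-hour reporting |
| Notes review (5.12) | 28 days, all participants | Framed as resource use, with no formal analysis planned (5.13) |
| Notes review (7) | Held after recruitment, once clinic letters are back | Its 28 days attach to medications prescribed, not to adverse events; too late for 24-hour reporting |

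Sample size, significance level and power are not affected.

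**The case against.** The best defence is that other routes run longer and apply to both arms. The diary can last four weeks, the resource-use review captures major events to 28 days for everyone, and the Section 7 notes review carries no seven-day limit of its own. The promise to collect severe antibiotic reactions has no window either. This stands in part: most major events should surface eventually in either arm. These routes do not replace prompt reporting of serious events.

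It can also be said that 7.4 is open-ended, and that diary-only side effects can coexist with practice-reported serious events. The second point is right, so 7.3 and 7.4 need not conflict. The first is weaker: the opening of Section 7 covers all adverse events and introduces the procedures that follow, so its end date governs them unless the text says otherwise.

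Three stronger readings are tempting, and the document does not support them.

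- A reader might infer that the intervention will look safer by construction. The window is formally the same in both arms, the diary and notes review soften the gap, and Section 9.1 describes no between-arm analysis of adverse events that it could bias.
- A reader might multiply the expected 65% antibiotic use by 54 per arm (108/2) and conclude that about 35 courses (0.65 × 54 = 35.1) go unobserved. That count includes early starters, whose courses fall partly inside the window, and 5.15 treats 65% as a figure to be reached or bettered.
- A reader might take it that delayed antibiotics normally start after the window. One trigger, worsening, has no waiting period, and no start-time distribution is given.

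**Conclusion.** The point holds, with moderate weight. On the practice-reporting route, the stated window covers the whole immediate control course, 7 of up to 21 irrigation days, and part or none of a delayed antibiotic course. Section 7 also contradicts itself on whether adverse events are reported at all, and its one-week limit does not match the 28 days used for major events in 5.12.

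This rests on three assumptions: the Section 7 window governs serious events because 7.4 gives no other; control participants start their course on the day of randomisation; and course days stand in for time at risk, so events that begin after a course ends are not counted. The 33% for irrigation is the lowest coverage, reached only by those who irrigate for the full 21 days. How many events would be missed cannot be derived from the protocol.

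**What to change.** Amend the safety wording as follows.

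- Set the reporting window for serious adverse events, serious adverse reactions and the severe antibiotic reactions named in Section 7 to day 28 after randomisation for all participants, keeping the 24-hour rule. This matches the maximum diary length and the resource-use review.
- State that non-serious side effects come from the diary, and that the notes review to day 28 is the back-up for events not otherwise notified.
- Reconcile the three conflicting statements: that all adverse events are to be reported, that they are not collected, and that side effects come from the diary alone. Each class of event should have one route and one end date.

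The cost is a protocol wording amendment and possibly a few more serious-event forms. The 28-day notes review is already planned. Treatment, sample size and the planned analyses do not change.
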